7.2 AE classification according to predictability

For the classification of predictability of AEs reported during the clinical trial, the Investigator will use the Investigator's Brochure (IB) as the reference safety document.

- **Unexpected:** an AE whose nature or intensity is not consistent with the information provided in the Investigator's reference safety document for the investigational product, meaning it is unexpected based on the product's characteristics;
- **Expected:** an AE whose nature or intensity is consistent with the information provided in the Investigator's reference safety document for the investigational product.

The expected AEs are referred to as "AEs of interest" because they are actively sought during clinical trials. They have been defined based on the results of previous animal studies and exploratory studies in humans. The expected AEs of the investigational product can be divided according to their origin (Table 1).

TABLE 1. POSSIBLE AE FROM THE IP

| Origin | Potential side effects |
|--|--|
| Local allergy reaction or sensibility due to formulation components | Pruritus, erythema, urticaria, skin rash, edema. |
| Outcomes based on systemic vasodilation | Headache, hypotension |
| Outcomes based on excessive local vasodilation | Priapism |
| Outcomes resulted from peptide excretion by the kidneys | Tubulopathy |
| Other effects, with no clear rationale, detected in preclinical studies. | Diarrhea |

Among the potential risks described above, two main effects were observed during preclinical studies: i) the development of renal tubulopathies, observed only in a study in rats with high systemic doses of BZ371A; ii) and diarrhea, observed in female pigs with topical application of IP. In addition to these AEs, in exploratory studies, pruritus was the only effect reported by study participants, with only one case of mild severity and complete spontaneous resolution identified.

Therefore, for safety monitoring during the clinical trial development, the evaluation of risks related to the proposed formulation containing BZ371A will be carried out through (I) clinical and physical assessment (demographic data, medical and current history, concomitant medications); (II) vital signs

(SBP, DBP, HR, RR and T oC) and anthropometric measurements; (III) complete physical examination, including genitalia; and (IV) laboratory analysis (Table 4).

CHART 4. IP MONITORING DURING CLINICAL STUDIES

| Possible AE | Monitoring |
|--|---|
| Unknown side effects | AE report and general physical exam; Complete blood count analysis, biochemistry, and urinalysis. |
| Local reaction: pruritus itching, redness, urticaria, skin rash, edema | Local physical evaluation (genitalia) |
| Hypotension (or arrhythmia caused by hypotension) | BP, HR (ECG) analysis |
| Priapism | Local physical evaluation (genitalia) |
| Tubulopathy | Biochemistry and urinalysis |
| Diarrhea | AE report |

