7.11 ANVISA notification

The sponsor must ensure that all relevant information about unexpected serious adverse events that are fatal or life-threatening occurring in the national territory are documented and notified to ANVISA, through an electronic form within a maximum of 7 (seven) consecutive days from the date of knowledge of the case by the sponsor. In addition, additional information about the follow-up of these adverse events must be included in the form within 8 (eight) consecutive days from the date of notification. All other serious unexpected adverse events, whose causality is possible, probable, or definite in relation to the investigational products, must be reported to ANVISA within 15 (fifteen) consecutive days from the date of knowledge of the case by the sponsor.

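### Section 7.2 treats monitored adverse events as expected ones and defines expected and unexpected so that they overlap; a serious listed event could therefore miss ANVISA notification

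*Combined protocol and SAP*

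**What the plan says.** Section 7.2 names the Investigator's Brochure as the reference for predictability and defines two classes against it. It then adds a statement of its own: "The expected AEs are referred to as 'AEs of interest' because they are actively sought during clinical trials". On the origin of the list it says: "They have been defined based on the results of previous animal studies and exploratory studies in humans". The next sentence refers the reader to Table 1 for the expected AEs, divided by origin. Three rows matter here:

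- "Outcomes based on excessive local vasodilation | Priapism"
- "Outcomes based on systemic vasodilation | Headache, hypotension"
- "Outcomes resulted from peptide excretion by the kidneys | Tubulopathy"

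No row carries a limit on intensity or seriousness. On human experience the same section says that "pruritus was the only effect reported by study participants, with only one case of mild severity and complete spontaneous resolution identified".

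Section 7.11 sets the ANVISA rule. Unexpected serious events that are fatal or life-threatening are notified within 7 days. For the rest, with a 15-day limit: "All other serious unexpected adverse events, whose causality is possible, probable, or definite in relation to the investigational products, must be reported to ANVISA". Sections 7.10 and 7.12 send serious events to the Ethics Committee and the sponsor within 24 hours, with no reference to expectedness.

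**The concern.** An event that a trial looks for is not thereby expected for regulatory reporting. The first label governs what is monitored; the second decides whether a serious case is notified quickly. Section 7.2 uses one list for both.

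Section 3.1 calls this the first human trial with the new formulation. A serious case of hypotension, priapism or tubulopathy would be among the most informative events it could produce, and all three are in the list that 7.2 calls expected. If an investigator or the sponsor codes by the name of the event, the protocol's wording supports the class that 7.11 leaves out of ANVISA notification.

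**Working it through.** The point concerns a classification rule. The plan states no figure to reproduce, and the check is a trace through the text.

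**Step 1: what the list rests on.** Table 1 has 5 local reactions (pruritus, erythema, urticaria, rash, edema), 2 systemic vasodilator effects (headache, hypotension), and priapism, tubulopathy and diarrhea: 5 + 2 + 1 + 1 + 1 = 10 terms. Section 7.2 ties three of them to an observation: pruritus in humans (one mild case), tubulopathy in rats at high systemic doses, and diarrhea in female pigs after topical use. For the other 10 − 3 = 7 the protocol names no observation with the product, although 7.2 calls its two preclinical findings the main ones, so others may exist. For the three terms at issue:

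| Term | Basis given in the protocol |
|---|---|
| Hypotension | Section 1.1 says that topical use did not cause it preclinically; Section 8.5.2 derives it from the nitric oxide pathway |
| Priapism | Section 1.1 describes it in humans for the native spider venom; Section 8.5.2 derives it from the nitric oxide pathway |
| Tubulopathy | Section 7.2 reports it only in rats at high systemic doses |

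Section 8.5.2 also says that preclinical work showed no local or systemic side effects of the product, which does not agree with the tubulopathy and diarrhea in 7.2. The evidence behind the expected list is therefore described inconsistently.

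**Step 2: the two definitions.** Let N mean that the event's nature agrees with the Brochure, and I that its intensity does. As written in 7.2:

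- unexpected = (not N) or (not I)
- expected = N or I

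| N | I | Meets unexpected? | Meets expected? |
|---|---|---|---|
| yes | yes | no | yes |
| yes | no | yes | yes |
| no | yes | yes | yes |
| no | no | yes | no |

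Two of the four combinations fall in both classes. A listed type of event with an intensity that does not fit is the second row, and the text does not say which class prevails.

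**Step 3: whether intensity can settle it.** Table 1 gives no intensity to compare with. The scale in 7.3 grades by how often a problem was present over the last 30 days, whereas the synopsis gives each participant 7 days in the study, after a single dose. Seriousness is judged separately, by outcome, in 7.5. So the protocol itself offers no firm basis for saying that a serious case exceeds the expected intensity.

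**Step 4: the filter.** Both ANVISA routes in 7.11 require the event to be unexpected. The causality rule does not compensate. Under 7.6, an event in the right time window, without a strong other cause and physiologically related to the product, is probable. The mechanism that makes priapism related also places it in Table 1. It can meet the causality condition of the 15-day route and still fail the condition of being unexpected.

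**Step 5: the other routes.** The Ethics Committee (7.10) and the sponsor (7.12) receive serious events within 24 hours whatever their expectedness.

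**The case against.** The strongest reply is that Table 1 does not decide expectedness. Section 7.2 opens by naming the Brochure, and both definitions are measured against it. Table 1 is titled as possible AEs, its column is headed as potential side effects, and the following text calls the entries potential risks. The intensity limb also gives a route to coding a serious event of a listed type as unexpected. And the sponsor, who holds the ANVISA duty, hears of every serious event within 24 hours.

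Much of this stands. A reader might infer that a serious priapism, hypotension or tubulopathy would be coded expected and would escape notification. The documents do not support that: the Brochure governs, its content is not available here, and a mismatch in intensity alone meets the unexpected definition. Only the weaker statement, that such an event could be coded expected, is supported.

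The reply does not remove the point. Section 7.2 states in its own words which AEs are expected. If the Brochure carries the same list, the gap is real; if it does not, protocol and Brochure conflict. The intensity limb is undercut by the overlap in the definitions. Early receipt by the sponsor does not help if the sponsor then applies the 7.11 filter to an event already coded expected.

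**Conclusion.** The point holds as a defect in the classification rule. The protocol merges a monitoring list with the expected class, and its two definitions overlap in two of four combinations. A serious event of a listed type could therefore be coded expected and miss the 7-day or 15-day ANVISA notification.

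Its reach is limited to that one route. No frequency can be put on it: the documents give no rate for any of these events, and the count of Table 1 terms does not measure how many serious events would go unnotified among 12 participants. The conclusion assumes that coding follows the event name in Table 1 or that the Brochure has a similar list; neither can be checked from the documents.

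Two further inferences should not be drawn. A reader might think that the results would present such an event as a predicted effect, but Section 9 lists seven descriptors for each AE and expectedness is not among them. A reader might also conclude that only effects already seen in humans may count as expected; the documents contain no such standard, and 7.2 openly draws on animal findings.

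**What to change.** In Section 7.2:

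1. Keep Table 1 solely as the list of AEs of interest for active monitoring, and state that a listing there does not make an event expected for 7.11.
2. Define expected as agreement with the Brochure in both nature and intensity, so that a mismatch in either makes the event unexpected. In the notation above, expected becomes N and I, the exact complement of the present unexpected definition, and no combination falls in both classes.
3. State which serious events, if any, the Brochure lists as expected.

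The cost is a few sentences and a check against the Brochure. Visits, sampling, sample size and the planned analysis do not change. The possible downside is an extra expedited report to ANVISA.

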7.3 AE classification according to intensity

The classification of the intensity of AEs will be performed according to the World Health Organization's grading of intensity for health conditions described below:

- Mild: a problem is present less than 25% of the time, with an intensity that a person can tolerate and that rarely occurs in the last 30 days.
- Moderate: means that a problem is present less than 50% of the time, with an intensity that interferes with people's daily life and that occasionally occurs in the last 30 days.
- Severe: means that a problem is present more than 50% of the time, with an intensity that partially alters people's daily life and that frequently occurs in the last 30 days.
- Complete impairment: means that a problem is present more than 95% of the time, with an intensity that completely alters the person's daily life and occurs every day in the last 30 days.
- Not specified: means that there is not enough information to specify the intensity.
- Not applicable: means that it is inappropriate to use a grading (e.g. menstrual functions).

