5.2 Safety analysis and tolerability procedures

5.2.1 *Clinical and physical evaluation*

Demographic data, medical history, current medication, and adverse events will be collected through direct interviews with the research participant and/or their family members when necessary. The use of any concomitant medication should be recorded, including its indication.

5.2.2 *Vital signs and anthropometric*

The collection of vital signs aims to detect the presence of any AE, especially hypotension. In order to evaluate safety, the following parameters should be collected and recorded: systolic blood pressure (SBP), diastolic blood pressure (DBP), heart rate (HR), respiratory rate (RR) and axillary temperature (T°C).

Before evaluation period, participants should remain at rest (sitting and without physical effort) for at least 5 minutes in a room at room temperature. Blood pressure measurement should be obtained in only one of the participant's arms (right or left), which should be selected as a reference for subsequent measurements. The examiner should perform three measures with an interval of one minute between them; the first measurement should be discarded and the real blood pressure that should be considered is the average between the last two measurements.

The normal values are: SBP between 90-140 mmHg and DBP between 60-90 mmHg. Values outside these ranges will be considered as medical history or AE (whether before or after IP administration) and should be reported as such if there is clinical significance in the physician's opinion.

Vital signs should be collected at V-1, V0, and V1. At V0, they will be collected before IP administration (concomitant with medical evaluation); and in 30, 60, 180, and 360 minutes after IP administration.

Arterial hypotension should be recorded as an AE. Its occurrence should be associated with the following values: 20 mmHg reduction in SBP, 10 mmHg reduction in DBP, and/or 20% increase in HR. These values should all be related to the data recorded on the same day, before IP administration.

Weight, height, and body mass index (BMI) will be measured only at V-1 for eligibility and characterization of the evaluated sample.

5.2.3 *Physical and genitalia exam*

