7.4 AE classification according to frequency

- Once: the AE occurred only once;
- Continuous: AE persists or worsens, without resolution between treatment courses or cycles;
- Intermittent: AE occurs and resolves during one treatment cycle/course, and then occurs again in another treatment cycle/course.

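### Section 7.3 intensity grades use an unstated time base and a 30-day look-back that do not fit a single-dose trial ending at D5–D9, and Section 9 matches neither 7.3 nor 7.5

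*Combined protocol and SAP*

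**What the plan says.** Section 7.3 takes its intensity scale from a World Health Organization grading for health conditions. Each of the four graded levels joins three conditions:

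| Level | Share of time | Impact | Frequency, last 30 days |
|---|---|---|---|
| Mild | under 25% | tolerable | rare |
| Moderate | under 50% | interferes with daily life | occasional |
| Severe | over 50% | partly alters daily life | frequent |
| Complete impairment | over 95% | completely alters daily life | daily |

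The severe level reads "Severe: means that a problem is present more than 50% of the time, with an intensity that partially alters" daily life, for a problem that "frequently occurs in the last 30 days". The top level reads "Complete impairment: means that a problem is present more than 95% of the time", for a problem that "occurs every day in the last 30 days". The section does not say what the percentage is a percentage of, or when an AE is to be graded. Two labels carry no grade: "Not specified: means that there is not enough information to specify the intensity", and a not-applicable label for cases where grading would be inappropriate.

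Section 7.4 has its own frequency code for an isolated event: "Once: the AE occurred only once". Section 3.1 describes a single topical dose at V0 and a final visit V1 between 5 and 9 days later. At V0, vital signs are taken before dosing and "in 30, 60, 180, and 360 minutes after IP administration" (Section 5.2.2), and the genital examination is repeated at 360 minutes (Section 5.2.3). Section 7.9 continues monitoring until symptoms resolve.

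Section 9 will report each AE with an intensity of mild, moderate or severe. It also gives its own list of what makes an event serious, although Section 7.5 already sets out seven criteria.

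**The concern.** A scale built on how much of a month a problem occupied measures burden over that month. It does not measure how bad an acute reaction was at its worst. After one topical dose, with six hours of observation and one later visit, the reactions of interest may last minutes or hours. A literal reader of 7.3 may then find no level that fits. Two careful readers may also pick different levels, because nothing says which of the three conditions prevails.

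Safety and tolerability is a primary goal (Section 2.1). Section 7.1 evaluates safety by the type, frequency and intensity of AEs, and Section 9 reports intensity for every AE. Expected AEs in Table 1 include headache, hypotension and priapism. The documents give no durations for these, so it is an assumption that they may be brief.

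**Working it through.** **Visit window.** Chart 1 gives V1 as D7 with an interval of ±2 days: 7 − 2 = 5 and 7 + 2 = 9. This reproduces the 5 to 9 days stated in Section 3.1.

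Section 7.3 names no base for the time share, so three candidates are tried.

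**Base 1: 30 days.** An AE present continuously from dosing has, by V1, a share of
- D5: 5/30 = 16.7%
- D7: 7/30 = 23.3%
- D9: 9/30 = 30.0%

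The severe clause needs more than 0.50 × 30 = 15 days, and the top clause more than 0.95 × 30 = 28.5 days. Neither can be met by V1. Follow-up under 7.9 could pass 15 days only if the AE lasted more than 15 − 9 = 6 to 15 − 5 = 10 days beyond V1.

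**Base 2: time since dosing.** The durations are illustrative, with onset at application. Share = duration / elapsed time.

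| Duration | 60 min | 180 min | 360 min | D5 (120 h) | D7 (168 h) | D9 (216 h) |
|---|---|---|---|---|---|---|
| 1 h | 100% | 33.3% | 16.7% | 0.8% | 0.6% | 0.5% |
| 6 h | 100% | 100% | 100% | 5.0% | 3.6% | 2.8% |
| 72 h | 100% | 100% | 100% | 60.0% | 42.9% | 33.3% |

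The time clause that is met depends on when the AE is graded. For the 72 h event it changes within the permitted V1 window, from the severe clause at D5 to the moderate clause at D7 and D9.

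**Base 3: the event's own duration.** Every continuous event is 100%, so the clause separates nothing.

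**Frequency clause.** This does not depend on the base. From D0 to D9 there are 10 calendar days, so an AE that starts after dosing can be present on at most 10 of the last 30 days by V1. Presence on all 30 days needs D0 to D29, which is 29 − 9 = 20 to 29 − 5 = 24 days beyond V1.

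**The conditions joined.** Take the 6 h event as a single occurrence on base 2.
- At 360 minutes its share is 100%. That rules out mild and also moderate ("Moderate: means that a problem is present less than 50% of the time"). A single event is not frequent, nor daily, over 30 days, which rules out severe and complete impairment. No level fits.
- At V1 its share is 2.8–5.0%, which meets the time clauses of both mild and moderate (they overlap below 25%). It takes one of these if its impact is tolerable or interferes with daily life.
- A reader who lets time share or impact decide could call the same event severe.

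Now take a single brief event that completely alters daily life, graded at V1. It exceeds the impact wording of mild, moderate and severe, and it fails the time clause of the top level on bases 1 and 2 and the frequency clause on any base. No graded level fits. The not-specified label is for missing information, and nothing is missing. If the event only partly alters daily life, it lies between moderate and severe, and 7.3 does not define where one ends and the other begins.

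**Section 9 against 7.3 and 7.5.** Section 9 has three grades and 7.3 has four. The seriousness lists compare as follows:

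| Criterion | 7.5 | Section 9 |
|---|---|---|
| Death | yes | yes |
| Life-threatening | yes | yes |
| Hospitalization | yes | yes |
| Disability | yes | yes |
| Congenital anomaly | yes | no |
| Suspected transmission of infection | yes | no |
| Clinically significant, needing intervention | yes | no |
| Abortion | no | yes |

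Four of the seven criteria are kept, three are omitted and one is added.

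**The case against.** The case for leaving 7.3 alone is reasonable. The scale has a named source. Thirty days is the only period the section mentions, so the other two bases and all event durations are the reviewer's assumptions. A single disruptive event can plausibly be called moderate, being short, interfering and occasional. Seriousness is judged separately under 7.5, hypotension has its own numeric definition in 5.2.2, and Section 9 describes each AE by duration, resolution and causality. Stating the base, the grading time and the governing clause would remove the ambiguity without a new scale.

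Most of this limits the consequence and leaves the defect in place. Naming 30 days as the base would leave the upper time clauses out of reach by V1. Making impact the governing clause would amount to the impact-based scale proposed here.

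A reader might also infer stronger conclusions, which the documents do not support:
- *The 6 h event slides from severe to mild.* On the joined reading it was never severe, because the frequency clause already failed. It moves from no fitting level to mild or moderate.
- *Any brief event that alters daily life is ungradable.* This is clear only when daily life is completely altered, because the moderate and severe impact wordings have no stated boundary.
- *No AE at all can meet the daily 30-day clause by V1.* Section 7.1 counts some worsening of pre-existing conditions as AEs, and such a problem could have been present throughout. The limit holds for AEs that start after dosing.
- *Intensity will be under-graded, or notification of serious events will fail.* No direction of error is shown, and Sections 7.10 to 7.12 do not depend on the Section 9 list. Section 7.2 uses intensity to decide whether an AE is unexpected, but what the Investigator's Brochure says about intensity is not in these documents.

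**Conclusion.** The point holds and should be fixed. The intensity scale does not fit a single-dose trial with its last visit at D5–D9.

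Two results need no assumed event duration and apply to AEs that start after dosing. By V1 such an AE can occupy at most 10 of 30 calendar days, and on a 30-day base its time share is at most 16.7–30.0%. The clauses for complete impairment, and the time clause for severe on that base, are therefore out of reach by then. Worsening of a pre-existing problem is an exception, and so is an AE followed under 7.9 well beyond V1.

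The dependence on grading time assumes time since dosing as the base, and the durations shown are illustrative. The absence of any fitting level is clear for a single brief event that completely alters daily life.

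Section 9 separately conflicts with 7.3 on the number of grades and with 7.5 on seriousness. The omission that matters most is the clinically significant event requiring intervention. Congenital anomaly is remote in a one-dose study that excludes pregnancy.

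The consequence is confined to AE labels in the results. Each AE in the 12 participants is also described individually, and no sample size, test or error rate is affected.

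**What to change.** Before data collection:
- Replace the Section 7.3 levels with one mild/moderate/severe scale defined by the worst impact on usual activity at any time during the event. Drop the time-share and 30-day clauses. Duration and frequency are already recorded separately under Section 9 and Section 7.4.
- Use the same three grades in Section 9 and in the CRF.
- Replace the seriousness list in Section 9 with a reference to Section 7.5, keeping abortion as an added item if the sponsor wants it.

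The cost is wording changes to the protocol, the analysis section and the CRF, with prior ethics committee approval as Section 8.1 requires. Some events may be graded higher than under the present text. Visits, samples and the number of participants stay the same.
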